2.4 Sampling scheme

2.4.1 Participant recruitment and informed consent

In liaison with Tshepong Hospital staff, a list of names of all medicine ward patients will be generated on recruitment days. This list will be then be placed in random order (via random number generation on Excel worksheet). Recruitment will begin with the first individual and proceed down the list until the enrollment target for the day has been met. Patients on the list who are already enrolled, already declined, or do not meet enrollment criteria will be excluded. Patients who meet the enrollment criteria will be invited to participate (Appendix A: S001 Screening, eligibility and Enrolment). This process will take place any time after admission and prior to release.

2.4.2 Randomization

The total sample size is 180 HIV-positive and 60 HIV-uninfected adults. There will be a total of four study arms comprising of two arms for HIV uninfected and two arms for PWH. We will

perform individual randomization blocked by HIV-status to enroll 30 HIV-uninfected adults per arm and 90 PWH per arm (Figure 2).

[figure not shown]

Figure 2: Randomization Study Arms for Home Link Intervention

1. Randomization of hospital patients for recruitment: On each participant recruiting day, a list of all medical ward patients will be generated, and each patient will then be randomly listed in order of planned recruitment. Patients will be approached at any time after admission if they are next on the list for recruitment until the enrolment target is reached for that day. A new list will be generated each day including only those patients admitted 2 days prior (or on Thursday, Friday and Saturday on Mondays).
2. Randomization to study arm: After informed consent and completion of baseline CRFs the participant will be randomized to care as usual or Home Link arm.

Randomization will be conducted immediately after eligibility criteria for the participant has been documented and informed consent has been signed. Participants will be randomized 1:1 to either the care as usual or the Home Link intervention arms using computer-generated random numbers, stratified by HIV-status.

A study staff member will SMS a dedicated study telephone number – staffed by someone not linked to any other aspect of the conduct of the study. Details of the eligible participant, including randomization group (1=living with HIV; 2=living without HIV), initials (first two letters of the first name and first two letters of the surname), age, and sex, will be sent via SMS to the randomizing team. A member of the randomizing team will then relay the allocation details (within 15 minutes) to the study staff member

who requested the randomization via SMS. Proof of randomization will be sent to the study staff member who will place the proof into the participants' study file.

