2.3.2 Exclusion criteria

- <18 years of age
- Length of stay <2 nights
- Unknown HIV status at the point of study screening and enrollment
- Failure by the patient or next of kin to provide informed consent to be followed up by study staff after discharge
- Residing outside of Matlosana sub-district
- Not speaking any of the languages spoken by the study team

Late exclusions occurring after enrolment

- Death prior to hospital discharge
- Discharged too late for the study team to deliver the intervention
- Transfer to another hospital
- Relocation outside of Matlosana sub-district at the point of discharge or within 7 days of discharge

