2.5.2 Home Link study arm

The Home Link intervention will be delivered by a **home visit team** including a primary care nurse and counselor trained in patient-centered counseling (Table 1). A rotating hospital-based doctor will be available for pre-home visit clinical file review and post-visit discussion, via cell phone, for decision making and input on patient care during a household visit. We have termed this individual a "**discharge officer**". The discharge officer will be a Tshepong clinician who is working in the hospital. Supporting Home Link is expected to take <30 minutes of the physician's time during the day. The team will also consult with a GCP-trained, PHRU research doctor based at Tshepong Hospital prior to household visits and for advice regarding referrals, discharge from home-based care, and other queries.

Table 1. Home Link intervention team key members

Team member	Training	Location of service	Role
Primary Care Nurse	Professional Nurse	Home visit team	Clinical assessment and management
Counselor	High school diploma	Home visit team	Patient-centered counseling & home needs assessment
Discharge officer	Medical doctor degree	Based at hospital	Clinical support (via cell phone)
PHRU research doctor	Medical doctor degree	Based at hospital	First point of contact for clinical support

The home care team will travel via car to the participant's house one week after discharge and every two weeks thereafter until completing 6 visits or the participant is discharged from the Home Link intervention based on the clinical assessments.

Home visits: Prior to team departure for a participant's home: the discharge officer and PHRU research doctor will review the participant's medical file, including retrieving laboratory results pending at the time of discharge or the prior home visit, and add any patient specific recommendations for assessments to the Patient Assessment Instrument (Appendix A) for the nurse to use at the household.

At the household, the team will use the Patient Assessment Instrument to document findings and guide decision making in the following areas:

Primarily provided by the primary care nurse

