2.7 Post-discharge follow-up

The primary outcome is mortality six months after hospital discharge. Secondary outcomes include mortality 12 months after hospital discharge, number of nights spent in a hospital,

number of ambulatory clinical encounters after the index hospitalization, and patient out-of-pocket costs for medical care. Outcomes will be assessed through scheduled contact and completion of a structured questionnaire with the participant or designated next of kin (either telephonic or in person if telephonic fails) at 8, 12, 26, and 52 weeks. Mortality will be further ascertained through a 26 and 52 week review of the Tshepong Hospital file (including the affiliated Klerksdorp hospital files) and matching of participant national identification numbers to the vital statistics register through consultation with the Department of Home Affairs. Repeat hospitalization will be ascertained using self-report / next of kin report and hospital records. Most subsequent hospitalizations can be expected to be at Tshepong Hospital due to the substantial distance to reach the next nearest hospital (>50 km to a lower level facility). In our prior experience we have observed rare use of alternative hospitals. Clinic visit data will be ascertained by self-report followed by verification through review of clinic paper or electronic (tier.net) records and National Health Laboratory Service electronic records (TrackCare).

Table 2. Scheduled visit windows

Visit name	Period	Primary goal
8 week follow-up	20 – 70 days	Maintain contact with participant
12 week follow-up	71-150 days	Assess care engagement, care satisfaction, mortality
26 week follow-up	151 – 245 days	Assess care engagement, , mortality; conduct psychosocial assessment
26 week hospital file review	>26 weeks post-hospital	Abstract care visits, re-admission, death
26 week Home Affairs vital status review	>26 weeks post-hospital	Match South African ID numbers
26 week care verification	>26 week post-hospital	Use electronic and paper files to verify self-reported clinic visits
52 week follow-up	365-455 days	Assess care engagement, mortality
52 week hospital file review	>365 days post-hospital	Abstract care visits, re-admission, death
52 week Home Affairs vital status review	>365 days post-hospital	Match South African ID numbers

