3.2 Study sample size justification

We propose to recruit a sample of 240 participants randomized 1:1 into care as usual and Care Link arms. The participants will be blocked to include 30 HIV-uninfected adults and 90 people living with HIV per arm. The sample size has been determined to be feasible given time and budget limitations while still providing insight into the efficacy. Using the base rate of mortality from our preliminary study of 26% and an alpha of 0.05 and a sample size of 120 split 1:1 in care as usual and Home Link arms we have represented power versus intervention arm mortality, with sub-group analysis limited to PWH, in Table 11. We note that the primary goal is feasibility and acceptability. We are appropriately powered only for a substantial decrease in mortality from 26% to 10%.

Table 9. Power by varying effect size on reducing post-hospital mortality

alpha	power	N	N1	N2	delta	p1	p2
.05	.1589	180	90	90	-.06	.26	.2
.05	.2527	180	90	90	-.08	.26	.18
.05	.3764	180	90	90	-.1	.26	.16
.05	.5212	180	90	90	-.12	.26	.14
.05	.6704	180	90	90	-.14	.26	.12
.05	.803	180	90	90	-.16	.26	.1
.05	.9019	180	90	90	-.18	.26	.08

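### Arms are allocated in hospital but primary-outcome deaths count only from discharge, so the compared groups are defined by a post-randomisation event

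*Combined protocol and SAP*

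**What the plan says.** Section 2.4.1 allows enrolment at any point between admission and release. Section 2.4.2 places allocation straight after that: "Randomization will be conducted immediately after eligibility criteria for the participant has been documented and informed consent has been signed". (The same section also puts it after the baseline forms; either way it is in hospital.) The result is sent by SMS to the requesting study staff member within 15 minutes, and proof goes into the study file.

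The outcome clock starts later. Section 2.7: "The primary outcome is mortality six months after hospital discharge". Section 2.3.2 lists exclusions that occur after enrolment. The first is "Death prior to hospital discharge"; the others are discharge too late for the intervention to be delivered, transfer to another hospital, and relocation at discharge or within seven days of it.

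On delivery, section 2.5.2 has the team travel to the participant's "house one week after discharge and every two weeks thereafter". It names a supporting doctor: "The discharge officer will be a Tshepong clinician who is working in the hospital". Section 2.6 has study staff determine the discharge date. Form D001 (Table 8) records discharge or in-hospital death, with its date, in both arms. Tables 3 and 6 give a chi-square test of six-month mortality by arm. No analysis population is defined and no analysis from randomisation is planned.

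**The concern.** Randomisation balances the arms at the moment of allocation. The primary analysis compares only those who later leave hospital alive, in time and to a local address. Membership of that group is settled after the arm is known to study staff, and nothing in the plan separates the discharge decision from the arm.

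Suppose patients in one arm tend to leave earlier or later than they otherwise would. A death that would have fallen on the ward, and been excluded, then falls at home and is counted, or the reverse. Total deaths after randomisation need not change at all. Applying every late exclusion identically in both arms does not prevent this, because the event that triggers the exclusion is itself what may shift. At stake is whether the six-month mortality contrast, the first primary objective in section 1.2, can be read as a randomised comparison, and whether the same sequence is carried into the full trial for which this pilot is to supply the protocol.

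**Working it through.** **Inputs.** Section 3.2: "Using the base rate of mortality from our preliminary study of 26% and an alpha of 0.05". The contrast is also from section 3.2: "We are appropriately powered only for a substantial decrease in mortality from 26% to 10" per cent. Section 2.4.2: "Participants will be randomized 1:1 to either the care as usual or the Home Link intervention arms". Table 9 uses 90 people with HIV per arm. (The text above that table mentions 120 in total; the table's 180 is used here.)

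**The plan's own figure.** Two-proportion normal approximation, two-sided, pooled variance under the null, no continuity correction:

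- Pooled rate = (0.26 + 0.10)/2 = 0.18.
- Null standard error = √(0.18 × 0.82 × 2/90) = 0.05727.
- Alternative standard error = √(0.26 × 0.74/90 + 0.10 × 0.90/90) = 0.05602.
- Power = Φ[(0.16 − 1.96 × 0.05727)/0.05602] = Φ(0.852) = 0.803.

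Table 9 gives .803. The other six rows also reproduce, so there is no error in the power table.

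**Case A: true 26% v 10%, and k Home Link deaths move from before to after discharge.** They enter both numerator and denominator, so the Home Link rate is (9 + k)/(90 + k).

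| k | Home Link rate | Power |
|---|---|---|
| 0 | 9/90 = 10.0% | 0.803 |
| 1 | 10/91 = 11.0% | 0.744 |
| 3 | 12/93 = 12.9% | 0.612 |
| 5 | 14/95 = 14.7% | 0.479 |

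**Case B: no true effect (26% in both arms), and k Home Link deaths move to before discharge and are excluded.** Expected deaths are 0.26 × 90 = 23.4, so the Home Link rate is (23.4 − k)/(90 − k).

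| k | Home Link rate | Apparent benefit | Two-sided rejection |
|---|---|---|---|
| 0 | 26.0% | 0 | 5.0% |
| 1 | 22.4/89 = 25.2% | 0.8 points | 5.2% |
| 3 | 20.4/87 = 23.4% | 2.6 points | 6.8% |
| 5 | 18.4/85 = 21.6% | 4.4 points | 10.3% |

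Exact binomial enumeration of the chi-square test agrees closely: power 0.756, 0.624 and 0.482 in case A; rejection 5.2%, 6.8% and 10.1% in case B.

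**Cost of counting everyone from randomisation.** Assume a share q of each arm dies between randomisation and discharge regardless of arm, and that 26% v 10% applies to those discharged. The rates become q + (1 − q) × 0.26 and q + (1 − q) × 0.10.

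| q | Rates | Power, 90 randomised per arm | Power, about 90 discharged per arm |
|---|---|---|---|
| 2% | 27.5% v 11.8% | 0.759 | 0.768 (92 randomised) |
| 5% | 29.7% v 14.5% | 0.694 | 0.717 (95 randomised) |
| 10% | 33.4% v 19.0% | 0.595 | 0.641 (100 randomised) |

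The documents give neither k nor q; both are assumptions.

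**The case against.** The strongest reply is that the causal link is not in the text. The allocation goes to a study staff member and into the study file; no section says that the clinicians who decide discharge are told. A reader might infer from section 2.5.2 that the discharge officer controls when a participant goes home. The documents do not support that. The Home Link duties listed are file review before a home visit and telephone advice, and no section gives this officer authority over discharge. Section 4 also sends pre-discharge findings from both arms to the officer, so in-hospital contact is not confined to Home Link. This stands: the mechanism is possible, not shown. Against it, no section masks ward staff or keeps discharge decisions independent of arm, and participants who know their arm can mention it.

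Second, the sizes are assumed, and small shifts do little to the false-positive rate (5.2% for one death). This also stands. The inpatient mortality of 17.2 to 29.6% in section 1.1 should not be read as the death rate between allocation and discharge: it covers whole admissions across the continent, including time before enrolment.

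Third, the route exists only because in-hospital deaths are excluded, so the point overlaps with any comment on the late exclusions. It does, and the two should be handled together.

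Fourth, section 3.2 calls feasibility and acceptability the primary goal, and section 5.5 says the sample may be too small to show a clear difference. That lowers the urgency. It does not remove the point, because sections 1.2 and 2.7 make six-month mortality a primary objective and the primary outcome.

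**Conclusion.** The structural weakness is established from the text: allocation precedes the start of the outcome clock, and those compared are selected by events after allocation. Whether this biases the result is not established. A reader might conclude that the mortality comparison is already invalid; the documents do not support that, because no section shows the arm reaching the discharge decision, and the direction could be either.

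The size is conditional. With 90 per arm, moving 1 to 5 Home Link deaths across the discharge date would cut power at the design effect from 0.80 to between 0.74 and 0.48, or raise the null rejection rate from 5% to between 5.2% and 10.3%. These figures rest on assumed one-arm shifts, the plan's 26% and 10%, and the subgroup with HIV only.

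Nor is the problem beyond repair. Post-discharge data alone cannot reveal it, but D001 captures the in-hospital deaths and discharge dates in both arms. The change is worth making because it is inexpensive, not because harm has been shown.

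**What to change.** 1. **Participants not yet randomised.** Keep consent and baseline forms in hospital, but request the allocation SMS only once the discharge decision is documented and before the participant leaves. In-hospital deaths and transfers then precede randomisation. Sections 2.5 to 2.5.2 describe no arm-specific step that must come before discharge, the first home visit is a week later, and the SMS reply takes 15 minutes, so nothing in delivery depends on earlier allocation. Allocating by telephone after the participant has left is not equivalent: it opens a new interval in which people may die, move or be unreachable.

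   *Cost.* A protocol amendment and tracking of discharges in real time. That is more than the plan now asks: section 2.6 sets no time limit, and section 3.4.1 allows three days to update the administrative database. Some consented participants may leave before allocation; they count as not randomised and should be reported. Relocation within seven days would still follow allocation, so item 2 is needed for it.

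2. **Participants already randomised in hospital.** Prespecify a sensitivity analysis of six-month mortality in all randomised participants, counted from randomisation and including in-hospital deaths. Take in-hospital dates from D001 and later vital status from the Home Affairs match, and state that this match covers late-excluded participants. Report by arm the number and reason of late exclusions and the time from randomisation to discharge; these show directly whether discharge timing differed.

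   *Cost.* One extra analysis and no new in-hospital form. The effect is diluted by deaths before home visits could act. The power loss is small if those deaths are few, and larger if they approach 10% of each arm, as shown in the working.

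Draft both items together with any revision of the late exclusions in section 2.3.2.

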2.5 Pre-discharge study procedures

All participants will have a baseline demographic health and psychosocial questionnaire (E001, E002).

2.5.1 Care-as-usual (CAU) study arm

Participants will receive standard discharge care as provided at Tshepong Hospital during the study. This currently includes discharge counseling from a trained discharge counselor and will be provided with a follow-up return date (usually two weeks post-hospital). Discharge counseling will include a review of discharge medications and instructions regarding follow-up care visits.

2.5.2 Home Link study arm

The Home Link intervention will be delivered by a **home visit team** including a primary care nurse and counselor trained in patient-centered counseling (Table 1). A rotating hospital-based doctor will be available for pre-home visit clinical file review and post-visit discussion, via cell phone, for decision making and input on patient care during a household visit. We have termed this individual a "**discharge officer**". The discharge officer will be a Tshepong clinician who is working in the hospital. Supporting Home Link is expected to take <30 minutes of the physician's time during the day. The team will also consult with a GCP-trained, PHRU research doctor based at Tshepong Hospital prior to household visits and for advice regarding referrals, discharge from home-based care, and other queries.

Table 1. Home Link intervention team key members

Team member	Training	Location of service	Role
Primary Care Nurse	Professional Nurse	Home visit team	Clinical assessment and management
Counselor	High school diploma	Home visit team	Patient-centered counseling & home needs assessment
Discharge officer	Medical doctor degree	Based at hospital	Clinical support (via cell phone)
PHRU research doctor	Medical doctor degree	Based at hospital	First point of contact for clinical support

The home care team will travel via car to the participant's house one week after discharge and every two weeks thereafter until completing 6 visits or the participant is discharged from the Home Link intervention based on the clinical assessments.

Home visits: Prior to team departure for a participant's home: the discharge officer and PHRU research doctor will review the participant's medical file, including retrieving laboratory results pending at the time of discharge or the prior home visit, and add any patient specific recommendations for assessments to the Patient Assessment Instrument (Appendix A) for the nurse to use at the household.

At the household, the team will use the Patient Assessment Instrument to document findings and guide decision making in the following areas:

Primarily provided by the primary care nurse

- (a) Assess illness severity. The nurse will assess for symptoms of COVID-19 infection and active TB disease as well as general illness severity using temperature, blood pressure, pulse, respiration rate, pulse oximetry, and orientation. Use of these signs will be guided by an algorithm (Appendix A) leading to (i) discharge from home visits, (ii) return visit in 2 weeks, (iii) contacting a clinician at Tshepong Hospital via cellphone for further guidance, or (iv) calling for routine medical transport (ambulance service) to transport the participant to Tshepong Hospital for evaluation and likely admission.
- (b) Medication reconciliation: review medication taking, medication availability, and prescribed medication plan. Counsel on appropriate dosing and address potential adherence barriers (e.g. lack of understanding, lack of medication availability, nausea or other side effects).
- (c) Obtain laboratory specimens (whole blood or urine, as required based on the discharge officer assessments) for transport to the laboratory and provide medications dispensed for the patient from the Tshepong Hospital pharmacy as indicated for a given participant.
- (d) Distribute any medications needed based on prescription from the discharge officer (based on a prior household visit assessment).

Primarily provided by counselor

- (e) Household assessment: assess for food availability and home support; (involve social workers at Tshepong Hospital if indicated) (completed during medical assessment).
- (f) Patient-centered counseling to address readiness for treatment engagement including readiness to accept treatment, readiness to face stigma and disclosure needs, building self-efficacy for care engagement, and providing counseling for symptoms of depression and/or alcohol abuse identified prior to hospital discharge or during home visits.
- (g) Participants who have low food security identified prior to hospital discharge will be provided with a food supplement/parcel at the first home visit.

At the conclusion of the home visit, the team will contact (phone call or text message) the hospital-based PHRU research doctor, if indicated, based on the Patient Assessment Instrument or if the team desires specific guidance. The PHRU doctor will have access to the hospital file (all files pulled prior to the visit) and will provide guidance to the team. The guidance will fall into one of four general categories: 1) make no changes, 2) adjust medication taking, 3) obtain laboratory specimens, or 4) refer to discharge officer for further guidance and/or hospital for probable admission.

The total time of the Home Link visit is anticipated to be 1 hour. The review with the doctor prior to departing for household visits is expected to take about 15 minutes and the mobile phone contact with the PHRU research doctor to be <10 minutes per household visit.

